For this study, MTD is defined as the dose that causes DLT (see section 4.1.3.3) in 10% of eligible cases. The trial will continue until a minimum of 12 subjects is treated. Six additional subjects might be accrued to obtain more data at the current MTD. The final MTD will be the dose with estimated probability of the DLT closest to the target toxicity rate of 10%.

Definition of a DLT

The timeframe for DLT evaluation is from day of infusion through 6 weeks post infusion.

Except as noted below, DLT will be defined as any of the following that may, after consultation with the FDA, be considered possibly, probably, or definitely related to the study cellular products:

- Grade 3 and 4 cytokine release syndrome (CRS*) that persists beyond 72 hours, or any Grade 5 CRS
- Any other ≥ Grade 3 non- hematologic toxicity, including allergic reactions to T cell infusions

*Grade 3 and 4 expected CRS reactions seen with the use of CAR-based immunotherapy such as (but not limited to) fever and hypotension requiring pressor support will not be considered a DLT unless it persists beyond 72 hours.

CRS toxicity will be graded according to the toxicity scale outlined in section 18.8 (APPENDIX VIII- CRS Toxicity Grading Scale and Management Guidelines).

Supportive Care

Subjects will receive supportive care for acute or chronic toxicity, including blood components or antibiotics, and other intervention as appropriate.

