4.1.4 Concomitant Medications/Treatments

Ideally, subjects should not receive other antineoplastic agents for at least 6 weeks post T cells (for purposes of evaluation) however, subjects with progressive disease may receive other therapy if needed at the discretion of their attending physician. If subjects receive other therapy adverse event reporting will cease after the initial 6-week assessments outlined in section 4.2 are completed. These subjects will continue to be monitored after PD according to the Time and Events Table in APPENDIX IV - Abbreviated Follow Up Required After Initiating Alternative Therapy (section 18.4).

If subjects experience PD after the initial 6-week assessment period following the cell infusion has been completed, they should be followed according to the Time and Events Table in APPENDIX IV - Abbreviated Follow Up Required After Initiating Alternative Therapy(section 18.4).

Confidential
Page 55 of 154

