- c. **RCR:** For replication competent retrovirus (RCR) testing, subject blood samples will be collected and stored pre-infusion. The pre-infusion sample will only be tested if the subject develops a long-term gene therapy side effect as described in Section 7.5.2. Additional samples for RCR testing will only be collected and subsequently analyzed in the event that the subject develops a long-term gene therapy side effect as described in Section 7.5.2.
- d. Cytokine Testing: Serum collected before and 3-4 hours after infusion for cytokine testing.
 - 12. Serum from blood drawn for functional studies at baseline and week 6 will be stored for measurement of human anti-mouse antibodies (HAMA). These studies will be performed in the event of a suspected immunologic reaction. See section 7.5.4 for additional details.
 - 13. Data on all adverse experiences/toxicities per CTCAE v4.0 regardless of seriousness must be collected for documentation purposes only for 6 weeks after dosing of the study drug/biologic. Adverse event data collection will cease in subjects that receive any other hemopoietic cell product or receive therapy for relapse of their primary malignancy. Data on disease status will continue to be collected as appropriate.

- a. If CRS signs and symptoms occur (see APPENDIX VIII- CRS Toxicity Grading Scale and Management Guidelines), a serum sample (~1 mL) for IL-6 analysis and 20 mL of blood should be collected before instituting treatment for CRS. Subsequent 20 mL blood samples should be collected once a day for the first 3 days. At the discretion of the sponsor, a daily sample may be requested for an additional 4 days. See section 7.5.6 for additional details.
- b. Serum (~1 mL) and 20 mL of blood should also be collected in the event of serious toxicities that develop that require hospitalization. Subsequent 20 mL blood samples should be collected once a day for the first 3 days. At the discretion of the sponsor, a daily sample may be requested for an additional 4 days. See section 7.5.6 for additional details.
- c. An additional blood sample of approximately 20 mL may be collected if any subject develops an AE or event of clinical significance that is thought to be at least possibly related to the CAR T cells.
 - 14. CoA generated at completion of required studies for production/QA of cells.

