9.2 Documentation of Non-Serious Adverse Events or SARs

For non-serious AEs or SARs, documentation shall begin at the time the main study consent form is signed by the subject prior to ATLCAR.CD30 infusion and continues through the 6 week follow-up period after treatment is discontinued. In addition, any AEs or SARs experienced by the subject related to the procurement procedure must also be documented.

Collected information should be recorded in the Case Report Forms (CRF) for that subject. Please include a description of the event, its severity or toxicity grade, onset and resolved dates (if applicable), and the relationship to the study drug. Documentation should occur at least monthly.

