10.2 Documentation of SAEs or Serious SARs

10.2.1 Timing

After informed consent but prior to initiation of study medications, only SAEs caused by a protocol-mandated intervention will be collected (e.g. SAEs related to invasive procedures such as biopsies, medication washout.

For any other experience or condition that meets the definition of an SAE or a serious SAR, recording of the event must begin from day 1 of study treatment and continue through the 6 week follow-up period after treatment is discontinued.

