18.4 APPENDIX IV - Abbreviated Follow Up Required After Initiating Alternative Therapy

Subjects should not receive other antineoplastic agents for at least 6 weeks post T cell infusion (for purposes of evaluation). Subjects who experience disease progression after a cell infusion may receive other therapy if needed at the discretion of their attending physician. If subjects receive other therapy they will come off study for adverse event reporting after the 6-week assessments outlined in section 4.2 are completed. Subsequent follow up assessments for subjects post progression are outlined in the table below. If subjects initiate alternative therapy after they have completed the initial 6-week follow up period for the cell infusion, they should be contacted as outlined below. The timing for each visit relates to the last cell infusion received by the subject. Follow up kits and instructions will be provided to subjects who initiate alternative therapy. Blood samples should be collected by a local health care provider as outlined in the laboratory manual.

Assessments ¹	Post Disease Progression Follow Up								
	Month 3 D1	Month 6 D1	Month 12 D1	Yearly					
History ²	Х	Х	Х	Х					
Performance status	X	Х	Х	Х					
Correlative Samples, ³	Х	Х	Х	Х					
Survival	X	Х	Х	Х					

Table 7	Abbreviated Follow-up	After Initiating Alternative	Therapy
	1	8	1.

Footnotes for the Abbreviated Follow-up After Initiating Alternative Therapy T&E Table

- 1. A window of +/-10 days will apply to the every 3 months study visits, and a window of +/-30 days will apply to visits separated by ≥ 6 months. Yearly follow-up visits are required during long-term follow-up for a total of 15 years or until death.
- 2. History and performance status information will be collected via the phone contact. Survival will also be documented. Medical history must include collecting the following information: 1. New malignancy(ies) 2. New incidence or exacerbation of pre-existing neurologic disorder 3. New incidence or exacerbation of a prior rheumatologic or other autoimmune disorder 4. New incidence of a hematologic disorder and 5. New incidence of infection (potentially product related).
- 3. Correlative analysis will include the following. Correlative blood sample collection will cease if the samples are no longer required for function and persistence or clonality analysis.

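### Footnote 13 of the Time & Events Table ends adverse event collection on relapse therapy or another cell product, even inside the 6-week DLT window, contrary to the rest of the protocol

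*Combined protocol and SAP*

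**What the plan says.** Footnote 13 is attached to the Toxicity row of the Time & Events Table, which ends at week 6. Its first sentence says that adverse event data "regardless of seriousness must be collected for documentation purposes only for 6 weeks after dosing of the study drug/biologic". Its second sentence is: "Adverse event data collection will cease in subjects that receive any other hemopoietic cell product or receive therapy for relapse of their primary malignancy".

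Elsewhere the protocol says:

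- **Section 4.1.4:** "If subjects receive other therapy adverse event reporting will cease after the initial 6-week assessments outlined in section 4.2 are completed". The same section accepts that other therapy may start early: "subjects with progressive disease may receive other therapy if needed at the discretion of their attending physician".
- **Appendix IV (18.4):** subjects who receive other therapy "they will come off study for adverse event reporting after the 6-week assessments outlined in section 4.2 are completed".
- **Section 9.2 (non-serious events):** documentation "continues through the 6 week follow-up period after treatment is discontinued".
- **Section 10.2.1 (serious events):** "recording of the event must begin from day 1 of study treatment and continue through the 6 week follow-up period after treatment is discontinued".
- **Section 4.1.3 (definition of a DLT):** "The timeframe for DLT evaluation is from day of infusion through 6 weeks post infusion".

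Section 11.1 feeds DLTs within 6 weeks into the CRM. A subject still in follow-up is temporarily scored as the fraction of the 6 weeks remaining.

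**The concern.** The only collection period that footnote 13 sets is 6 weeks. Within the footnote, a rule that ends collection can therefore act only before week 6, which is inside the DLT window. Delayed events are handled separately in footnote 17. Section 4.1.4 does not settle the matter, because it defers to the assessments in section 4.2, the table that carries footnote 13.

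The DLT rate is the primary endpoint and determines dose assignment. Section 11.1 does not say how to score a subject whose collection stops early. If that subject is counted as DLT-free and a later DLT went unrecorded, the DLT rate is biased downward. If the subject had no DLT but is left at the temporary fraction, it is biased upward.

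Harm requires three things together: other therapy before week 6, a site that follows footnote 13 over the other sections, and either a later event that meets the DLT definition or a wrongly retained fraction. Serious events (10.2.1), deaths within 30 days, and Grade 4 or greater infusion reactions, CRS and neurologic toxicity (10.3.3) would still be captured. The main exposure is related non-hematologic toxicity of Grade 3 or higher that does not meet the seriousness criteria.

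**Working it through.** **Step 1. The texts side by side.**

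| Place | When collection ends if other therapy starts before week 6 |
|---|---|
| 4.2, footnote 13 | When that therapy or cell product is given |
| 4.1.4 | After the 6-week assessments |
| Appendix IV | After the 6-week assessments |
| 9.2 | End of 6 weeks; no exception stated |
| 10.2.1 | End of 6 weeks; no exception stated |
| 4.1.3 (DLT window) | End of 6 weeks; no exception stated |

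The conflict with 4.1.4 and Appendix IV is explicit. The conflict with 9.2 and 10.2.1 is by omission. Section 4.1.4 and Appendix IV do not name another hemopoietic cell product, so for that trigger the conflict rests on 9.2, 10.2.1 and the DLT window.

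**Step 2. The plan's own figure.** Section 11.1 scores a subject followed for 2 of 6 weeks as 1 - 2/6 = 2/3 of a DLT. This reproduces.

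**Step 3. What one lost event does to the CRM.** Inputs from section 11.1: p_i = a_i^b, a = (0.0281, 0.0568, 0.1), b exponential with mean 1, target 0.10. Assumed data: 0/2 at level 1, 0/2 at level 2 and y/k at level 3, so the total is k + 4 subjects. The posterior for b is proportional to exp(-b) times the product over levels of p_i^y_i (1 - p_i)^(n_i - y_i). The documents do not say which estimator is used, so two are shown: plug-in, a_i^E(b), and posterior mean, E(a_i^b). The prescribed level is the one closest to 0.10.

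Worked plug-in case, k = 2:

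- y = 0: E(b) = 1.724, level 3 estimate 0.1^1.724 = 0.019; level 3 is prescribed.
- y = 1: E(b) = 0.772, level 3 estimate 0.1^0.772 = 0.169, level 2 estimate 0.0568^0.772 = 0.109; level 2 is prescribed.
- y = 2/3: E(b) = 0.931, level 3 estimate 0.1^0.931 = 0.117, level 2 estimate 0.069; level 3 is prescribed.

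Over k = 2 to 14 (6 to 18 subjects):

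| Truth vs what is scored | Plug-in | Posterior mean |
|---|---|---|
| 1 DLT vs 0 | Level 2 vs 3 for k = 2-4; level 3 in both for k = 5-14 | Level 1 vs 3 for k = 2-4; 2 vs 3 for k = 5-7; level 3 in both for k = 8-14 |
| 2 DLTs vs 1 | Differs for k = 2-12 (at k = 8-12, level 2 vs 3); same for k = 13-14 | Differs for k = 5-14 (at k = 8-9, level 1 vs 3; at k = 10-14, level 2 vs 3) |
| 0 DLTs vs 2/3 retained | Level 3 in both for all k | Level 3 vs 1 at k = 2; 3 vs 2 for k = 3-5; level 3 in both for k = 6-14 |

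Where the level does not change, the estimate still does. With one unrecorded DLT, the plug-in estimate at level 3 falls from 0.086 to 0.009 at k = 8 (12 subjects) and from 0.057 to 0.006 at k = 14 (18 subjects).

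**Step 4. How often.** The documents give no rate of early other therapy. The first scheduled post-infusion scan is at 6-8 weeks, so the rate should be low. Assume 2-15% of 12-18 subjects:

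- Subjects affected: 12 x 0.02 = 0.24 to 18 x 0.15 = 2.7.
- Expected unrecorded DLTs at the 10% target rate: 0.24 x 0.10 = 0.024 to 2.7 x 0.10 = 0.27.

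This is an upper bound for the assumed range, because it places all of each affected subject's DLT risk after the start of other therapy and credits no capture as an SAE.

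**The case against.** The strongest reply is that the footnote is shorthand for section 4.1.4 and merely omits a reference to week 6. Section 11.3.1 summarises adverse events in long-term follow-up, footnote 17 and section 7.4 record delayed events, and 4.1.4 itself presupposes that reporting can otherwise run past week 6. DLT detection also has other supports: toxicity assessments listed at weeks 1, 2, 4 and 6 with no exception for other therapy, the real-time toxicity monitoring in 11.1, and the Principal Investigator's continuous monitoring in 10.4. Early other therapy is discouraged in both 4.1.4 and Appendix IV.

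Much of this stands as an argument about probability. A missed DLT needs one footnote sentence to prevail over several other provisions. It does not remove the conflict, because the harmonising reading depends on a time limit that the footnote lacks and that the fix would supply.

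Two objections to the illustration also stand in part. The late two-DLT states arise only under some orders of events, since an early recorded DLT would already have moved the next assignment below level 3. And the fraction in 11.1 is described as temporary, so keeping it is only one reading of a silence in the text.

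**Conclusion.** The concern holds. Footnote 13 conflicts directly with section 4.1.4 and Appendix IV, and by omission with sections 9.2 and 10.2.1. Followed as written, it can cut short the data behind the primary endpoint.

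The expected loss is small: at most 0.02 to 0.27 unrecorded DLTs, given the assumed 2-15% rate of early other therapy and a 10% DLT rate. The effect of a single loss is not always small. On the assumed data, one unrecorded DLT changes the prescribed level at 6-8 subjects in total (plug-in) or 6-11 (posterior mean). If it is the second of two DLTs, the level can still differ at 12-16 subjects (plug-in) or 12-18 (posterior mean). This should be fixed; it is not a fatal flaw in the design.

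**What to change.** Reconcile footnote 13 with 4.1.4, Appendix IV, 9.2 and 10.2.1. State that adverse event and DLT data are collected through 6 weeks post infusion in every infused subject, whatever other therapy or cell product is given, and that other therapy ends collection only after week 6. Record the start date of other therapy so that attribution can be judged. No subject would then lose DLT follow-up for this reason, so section 11.1 would need no scoring rule for it; incomplete follow-up from other causes, such as withdrawal, is a separate matter.

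The cost is one footnote sentence and a few more weeks of adverse event entry in a few subjects, at visits already scheduled. The change concerns data collection only and does not touch when other therapy may be given.

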5.0 STUDY POPULATION

Unless otherwise noted, subjects must meet all of the following criteria to participate:

5.1 Inclusion Criteria for Prior to Cell Procurement

- 1. Informed consent explained to, understood by and signed by subject/guardian; subject/guardian given copy of the procurement/screening informed consent.
- 2. 3 to 17 years of age for pediatric subjects, ≥18 years of age for adults; NOTE: children will not be allowed to enroll in a dose cohort until a minimum of 2 adult subjects were enrolled and complete their DLT assessment follow-up at that dose level.
- 3. Diagnosis of recurrent HL with a treatment plan that will include high dose chemotherapy with/without total body irradiation and autologous cell transplantation.
- 4. NHL subjects with ALK negative CD30+ anaplastic large-cell lymphomas, CD30+ ALCL regardless of ALK status, with chemotherapy-sensitive relapse, CD30+ highrisk DLBCL, CD30+ cutaneous T cell lymphoma, or CD30+ mycosis fungoides who are otherwise eligible for transplant, are eligible for this study.
- 5. Karnofsky or Lansky score of > 60% (APPENDIX III- Lansky and Karnofsky Performance Status)
- 6. Evidence of adequate organ function as defined by:

The following is required prior to procurement (NOTE: labs do not need to be redrawn if they have already been performed as part of SOC pre-transplant work-up; Subject must be eligible to receive ASCT)

- Hgb ≥ 8.0 g/dL
- Bilirubin ≤ 1.5 times the upper limit of normal (ULN)
- AST \leq 3 times ULN
- Serum creatinine ≤ 1.5 times ULN
- Cardiac and pulmonary function that is adequate for ASCT
- 7. In women of child-bearing potential (WOCBP), a negative serum pregnancy test within 72 hours prior to procurement. WOCBP are those who have not been surgically sterilized or have not been free from menses for > 1 year.

8. Considered at high risk for relapse as defined by:

The presence of ≥ 1 of the following: failure to achieve CR post initial treatment; relapsed disease with an initial remission duration of <12 months; or extranodal involvement at the start of pre-transplant salvage therapy.

9. WOCBP should be willing to use 2 methods of birth control or be surgically sterile or abstain from heterosexual activity for the course of the study, and for 6 months after the study is concluded. WOCBP are those who have not been surgically sterilized or have not been free from menses for > 1 year. The two birth control methods can be composed of: two barrier methods or a barrier method plus a hormonal method to prevent pregnancy. The male partner of WOCBP subjects enrolled into the trial should be instructed to use a condom by their female partner enrolled in the trial.

5.2 Inclusion Criteria Prior to Infusion of ATLCAR.CD30 Cells

- 1. Informed consent explained to, understood by and signed by subject/guardian; subject/guardian given copy of informed consent.
- 2. 3 to 17 years of age for pediatric subjects, ≥18 years of age for adults; NOTE: children will not be allowed to enroll in a dose cohort until a minimum of 2 adult subjects were enrolled and complete their DLT assessment follow-up at that dose level.
- 3. Diagnosis of recurrent HL with a treatment plan that will include high dose chemotherapy with/without total body irradiation and autologous cell transplantation.
- 4. NHL subjects with ALK negative CD30+ anaplastic large-cell lymphomas, CD30+ ALCL regardless of ALK status, with chemotherapy-sensitive relapse, CD30+ highrisk DLBCL, CD30+ cutaneous T cell lymphoma, or CD30+ mycosis fungoides who are otherwise eligible for transplant, are eligible for this study.
- 5. CD30+ disease (result can be pending at the time of cell procurement, but must be confirmed prior to treatment with ATLCAR.CD30 cells); NOTE: CD30+ disease requires documented CD30 expression by immunohistochemistry based on the institutional hematopathology standard.
- 6. Evidence of adequate organ function as defined by:

The following is required prior to infusion of ATLCAR.CD30 cells:

• Absolute neutrophil count (ANC) ≥500 cells/mm3 for 3 consecutive days; Note: ANC may be measured at the beginning and the end of a time frame expanding at least 3 days and does not need to be evaluated on each individual day **AND**

- Platelet count ≥25,000 cells/mm3 without transfusion over preceding 5 days; Note: Platelets may be measured at the beginning and the end of a time frame expanding at least 5 days and does not need to be evaluated on each individual day **AND**
- Hg \geq 8g/dL without transfusion support over preceding 5 days; Note: Hg may be measured at the beginning and the end of a time frame expanding at least 5 days and does not need to be evaluated on each individual day
- Bilirubin ≤ 1.5 times the upper limit of normal (ULN)
- AST \leq 3 times ULN
- Serum creatinine ≤1.5 times ULN
- Pulse oximetry of > 90% on room air
- 7. Imaging results from within 60 days prior to transplant (used as baseline measure for documentation of disease status).
- 8. In women of child-bearing potential (WOCBP), a negative serum pregnancy test within 72 hours prior to procurement and again 72 hours prior to infusion is required.
- 9. Karnofsky or Lansky score of > 60% (APPENDIX III- Lansky and Karnofsky Performance Status)
- 10. Considered at high risk for relapse as defined by:
 - The presence of ≥ 1 of the following: failure to achieve CR post initial treatment; relapsed disease with an initial remission duration of <12 months; or extranodal involvement at the start of pre-transplant salvage therapy.
- 11. Subjects must have autologous transduced activated T-cells that meet the Certificate of Analysis (CoA) acceptance criteria.
- 12. WOCBP should be willing to use 2 methods of birth control or be surgically sterile, or abstain from heterosexual activity for the course of the study, and for 6 months after the study is concluded. WOCBP are those who have not been surgically sterilized or have not been free from menses for >1 year. The two birth control methods can be composed of: two barrier methods or a barrier method plus a hormonal method to prevent pregnancy. The male partner of WOCBP subjects enrolled into the trial should be instructed to use a condom by their female partner enrolled in the trial.

5.3 Exclusion Criteria

Subjects meeting any of the following exclusion criteria will not be able to participate in this study:

- 1. Received any investigational agents or received any tumor vaccines within the previous six weeks prior to cell infusion.
- 2. Received anti-CD30 antibody-based therapy within the previous 4 weeks prior to cell infusion
- 3. Pregnant or lactating
- 4. Tumor in a location where enlargement could cause airway obstruction.
- 5. Current use of systemic corticosteroids at doses >10mg/day prednisone or its equivalent; those receiving ≤ 10 mg may be enrolled at discretion of investigator.
- 6. Active infection with HIV, HBV, HCV (can be pending at the time of cell procurement; only subjects meeting the criteria as so described will be infused). Note: To meet eligibility subjects are required to be negative for HIV antibody, negative for Hepatitis B surface antigen, and negative for HCV antibody or viral load.

